4.2 PROHIBITED MEDICATIONS

Medications or vaccinations specifically prohibited in the exclusion criteria (see Section 2.1.2) are not allowed during the ongoing trial. If there is a clinical indication for a prohibited medication/measure during the trial, discontinuation from trial therapy may be required, but the participant may remain on study for follow up. The following treatments should not be administered during the trial:

- Other immunotherapies or immunosuppressive drugs (for example, chemotherapy or systemic glucocorticoids except for prophylaxis or treatment of allergic reactions, endocrine replacement therapy as low dose prednisone [≤ 10 mg daily] or equivalent, for the treatment of irAEs, or for short courses (≤ 14 days) as appropriate medical therapy for unrelated medical conditions (e.g., asthma). Glucocorticoids with no or minimal systemic effect (topical, inhalation) are allowed.
- Prophylactic use of glucocorticoids for infusion related reactions. **NOTE:** Glucocorticoid administration prior to CT scans in participants with intravenous contrast allergy is allowed.
- Any live vaccine therapies for the prevention of infectious disease. Examples of live vaccines include, but are not limited to, the following: measles, mumps, rubella, varicella/zoster, yellow fever, rabies, BCG, and typhoid vaccine. Administration of inactivated vaccines is allowed (for example, inactivated influenza vaccines, recombinant zoster vaccine, or locally approved COVID vaccines).
- Systemic anticancer treatment.

5 CORRELATIVE STUDIES FOR RESEARCH

5.1 SUMMARY

A description of research correlative studies including a brief statement of rationale and processing information is provided below. The list is not all inclusive and studies may or may not be performed in select participants based on investigator discretion and available resources. Studies may include, but are not limited to, the following:

Test / Assay	Collection Details (approx. volume, tube type ¹⁾	Collection Time (+/- 48hrs)	Location of Specimen Analysis	Storage
Tumor Tissue				
Sequencing, gene expression analysis, proteomics, and methylation	FFPE / snap frozen tissue Tumor tissue	See Study Calendar	NIDCD or NFGCF	NIDCD tissue repository
Immune markers (IHC)			GMB TIME Lab, [name] Lab	
Organoid cultures			[name] Lab	
Cell line and participant derived xenograft development			[name] Lab and NCI PDM	
RNA expression level of 770 genes			LTIB and NFGCF	
T cell clonality (ImmunoSeq)				
Blood Samples				
WBC DNA Sequencing ³	60-80 mL blood for PBMCs, Sodium Heparin tubes (green top)	See Study Calendar	NFGCF	CSP
Standard and 123 immune cell subsets (FACS)			LTIB	
Functional Analysis of immune cell subsets (FACS)				
Antigen Specific Immune Response (Cytokine Staining Assay)				
T cell clonality (ImmunoSeq)			LTIB and NFGCF	

RNA expression level of 770 genes				
Soluble factors (incl. sCD27, sCD40L, ELISA)	8 mL blood for serum, SST		LTIB	
Circulating free tumor DNA(PCR)	10 mL (Streck tubes)		LTIB and NIH Core Facility	CSP
Extracellular/ exosome DNA	10 mL (Streck tubes)		[name] Lab	
Pharmacokinetics/ADA(ELISA)	8 mL blood for serum (SST)		EMD Serono	CSP
TGF β 1 levels (ELISA/bead based multiplex assay)	10 mL EDTA lavender top tube		LTIB	CSP

¹ Tubes/media may be adjusted at the time of collection based upon materials available or to ensure the optimal samples are collected for planned analyses.

² LTIB: Laboratory of Tumor Immunology, NIDCD: National Institute of Deafness and Craniofacial Disorders, NFGCF: NCI Frederick Genomic Core Facility; NCI Participant-Derived Models Repository: NCI PDM; SST: serum separation tubes

³ Control for sequencing studies of tumor, circulating tumor DNA, and extracellular/exosome DNA

Research blood samples will be sent to the Clinical Services Program – Leidos Biomedical Research, Inc. (CSP) for barcoding, initial processing and storage. Tissue will be sent to the NIDCD tissue repository. From these facilities, coded, linked samples will be sent to the designated labs for analysis upon request

5.2 SAMPLE COLLECTION AND PROCESSING

For the planned analyses described below, laboratories may share resources or collaborate if appropriate. Portions of all samples may be banked for future research analyses; prospective consent will be obtained during the informed consent process.

For adult subjects: The amount of blood that may be drawn from adult participants for research purposes shall not exceed 10.5 mL/kg or 550 mL, whichever is smaller, over any eight-week period.

5.2.1 Peripheral blood collection

Subjects will have approximately 130 mL of peripheral blood drawn at each time point specified in Study Calendar [3.7](#) (six to eight, 10-mL green top sodium heparin tubes for PBMC samples, two 8-mL serum-separating tube for serum samples, three 10-mL lavender EDTA tubes).

5.2.1.1 Immune Phenotyping – PBMCs

Where possible, exploratory immunologic studies will be conducted to evaluate the study drug's effect on the immune response before and after treatment, to gain insight into potential biomarkers, and help improve the administered therapy. Blood will be collected as per [Study Calendar](#). The following immune assays may be performed at the Laboratory of Tumor Immunology and Biology (LTIB) at the NCI's Center for Cancer Research (CCR) in select participants where adequate samples are available:

1. PBMCs may be analyzed for changes in standard immune cell types (CD4 and CD8 T cells, natural killer [NK] cells, regulatory T cells [Tregs], myeloid-derived suppressor cells [MDSCs], and dendritic cells) as well as 123 immune cell subsets, using multi-color flow cytometry.
2. PBMCs from selected subjects may be analyzed for function of specific immune cell subsets, including CD4 and CD8 T cells, NK cells, Tregs, and MDSCs using flow-based assays.
3. PBMCs may be analyzed for tumor antigen-specific immune responses using an intracellular cytokine staining assay. PBMCs will be stimulated in vitro with overlapping 15-mer peptide pools encoding tumor-associated antigens; control peptide pools will involve the use of human leukocyte antigen peptide as a negative control and CEFT peptide mix as a positive control. CEFT is a mixture of peptides of CMV, Epstein-Barr virus, influenza, and tetanus toxin. Post-stimulation analyses of CD4 and CD8 T cells will involve the production of IFN- γ , IL-2, TNF, and the degranulation marker CD107a. If sufficient PBMCs are available, assays may also be performed for the development of T cells to other tumor-associated antigens.
4. Changes in T-cell clonality score using Adaptive Biotechnologies TCR-seq assay.
5. Changes in inflammatory gene signature using Nanostring's nCounter Human PanCancer Immune Profiling Panel.

5.2.1.2 Soluble Factors

Samples for soluble factor analysis will be collected as per Study Calendar (Section [3.7](#)).

Where possible, sera and/or plasma may be analyzed pre- and post-therapy for the following soluble factors: sCD27, sCD40 ligand using commercial ELISA kits. Also, sera and/or plasma

may be analyzed for changes in cytokines (IFN- γ , IL-10, IL-12, IL-2, IL-4, etc.), chemokines, antibodies, tumor-associated antigens, and/or other markers using ELISA or multiplexed assays (e.g., Mesoscale, Luminex, cytokine bead array).

5.2.2 Tumor tissue samples

Archival tumor samples will be requested, where available. For participants with lesions amenable to biopsy, tumor biopsies will be performed (see Section 2.4 and Study Calendar 3.7). Selection of site for biopsy will be as per Section 2.4; an attempt will be made for site-matching between pre-treatment and on-treatment tumor biopsies. The biopsy will be performed per routine standard of care, by ENT/Surgery consultants or Interventional Radiology, with Imaging guidance (e.g., ultrasound or CT) as appropriate. Conscious sedation may be used, if warranted, and the use and risks to the participant are minimal. Endoscopy, CT or other imaging guidance will be used as appropriate. If these procedures are not considered to be of minimal risk to the participant, the biopsy will not be performed, and this will not be reported as a deviation of the protocol. The participant will consent at the time of the procedure. For the biopsies, if the participant refuses, the refusal will be documented in the medical record and in the research record.

Tumor samples will be sent to the Laboratory of Pathology for disease evaluation; remaining samples will be used for research. Tissue samples for research may also be stored in the NIDCD tissue repository.

5.2.2.1 RNA and T-cell Receptor Clonality Analysis of Blood and Tumor Tissue

Where possible, RNA expression and T-cell receptor clonality analysis will be done on the peripheral blood as well as archived tumor tissue or optional biopsies to help further evaluate changes in immune response and RNA expression levels with treatment as well as to determine tumor and infiltrating lymphocyte characteristics which may be predictive of response to treatment. In addition, these analyses will also be used to gauge resistance mechanisms and additional targets for future therapy. Coded, linked samples may be analyzed for RNA expression levels using the Nanostring platform and T-cell receptor clonality using the ImmunoSeq platform (LTIB and NCI Frederick Genomic Core Facility).

5.2.2.2 Bintrafusp alfa Pharmacokinetics

Serum PK measurements of Bintrafusp alfa (schedule per [Study Calendar](#)) may be measured. Coded, linked samples will be shipped to EMD Serono for analysis under existing CRADA, to collect data which will provide insight into population PKs of bintrafusp alfa in participants receiving these novel combinations.

5.2.2.3 ADA

Anti-Drug Antibody (ADA) development may lead to loss of efficacy of administered monoclonal antibodies. Measuring titers (schedule per [Study Calendar](#)) will examine if lack of efficacy of bintrafusp alfa is due to ADA development. Serum samples may be analyzed by EMD Serono with ELISA, under existing CRADA.

5.2.2.4 Analyses of Tumor Tissue for Immune Markers

Study of immune infiltration as well as immune mediated pathways such as PD-L1 status within the tumor microenvironment pre vs. post treatment by IHC and/or multiplex immunofluorescence may be performed by the GMB TIME Lab or by [name] (NIDCD). Where available, archival tumor samples may be requested for pre-treatment analysis (preferably tissue samples

from the last 6 months). For participants with lesions amenable to biopsy, biopsies may be performed as described in Section [5.2.2](#).

5.2.3 Sequencing, gene expression analysis, proteomics, and methylation

Studies characterizing the mutations, gene expression profile, protein analysis, and methylation status of ONB specimens will be performed at the NIDCD genomics core facility. Tissue samples for research will be stored and obtained from the NIDCD tissue repository.

5.2.4 Organoid cultures

Organoid cultures will be established from tissue specimens in the lab of [name]. This will be performed as recently described ([67](#)). Specimens directly from either core needle biopsy or endoscopic nasal biopsy will be utilized to generate these organoids *in vitro*. The organoids will be utilized to test novel immunotherapeutic approaches as well as interrogate and investigate alternative mechanisms of tumorigenesis such as epigenetic regulators and assess the effects of small molecule inhibition of these pathways.

5.2.5 Blood genomic material

WBC DNA as a control for sequencing studies as well as circulating tumor DNA and extracellular vesicle/exosome DNA will be analyzed in this portion of the protocol. Blood will be collected according to the study calendar and transferred to the LTIB. Genomic material may be used as a control for sequencing studies. Furthermore, serum and genomic materials may be collected to study circulating tumor DNA.

It is the intent and purpose of the subcontractor to accept only coded, linked samples and sample information. To the limit of our ability, every effort will be made to ensure that protected information is not sent electronically or by hard copy or on vial labels.

Sample data is stored in the Biospecimen Inventory System II (BSI). This inventory tracking system is used to manage the storage and retrieval of specimens as well as to maintain specimen data. BSI is designed for controlled, concurrent access. It provides a real-time, multi-user environment for tracking millions of specimens. The system controls how and in what order database updates and searches are performed. This control prevents deadlocks and race conditions. For security, BSI has user password access, 3 types of user access levels, and 36 user permissions (levels of access) that can be set to control access to the system functions. BSI provides audit tracking for processes that are done to specimens including shipping, returning to inventory, aliquoting, thawing, additives, and other processes. BSI tracks the ancestry of specimens as they are aliquoted, as well as discrepancies and discrepancy resolution for specimens received by the repository. If a specimen goes out of the inventory, the system maintains data associated with the withdrawal request. Vials are labeled with a unique BSI ID which is printed in both eye-readable and bar-coded format. No participant-specific information is encoded in this ID.

Investigators are granted view, input, and withdrawal authority only for their specimens. They may not view specimen data or access specimens for which they have not been authorized. Access to specimen storage is confined to repository staff. Visitors to the repositories are escorted by repository staff at all times.

5.3.3 Protocol Completion/Sample Destruction

All specimens obtained in the protocol are used as defined in the protocol. Any specimens that are remaining at the completion of the protocol will be stored in the conditions described above. The study will remain open so long as sample or data analysis continues. Samples from consenting subjects will be stored until they are no longer of scientific value or if a subject withdraws consent for their continued use, at which time they will be destroyed.

If the participant withdraws consent the participants data will be excluded from future distributions, but data that have already been distributed for approved research use will not be able to be retrieved.

The PI will record any loss or unanticipated destruction of samples as a deviation. Reporting will be per the requirements of Section [7.2](#).

5.4 SAMPLES FOR GENETIC/GENOMIC ANALYSIS

5.4.1 Description of the scope of genetic/genomic analysis

The research correlates for this study are expected to include DNA/RNA sequencing of tumors, including circulating tumor (ct) DNA. In addition, whole exome sequencing may include evaluation for known cancer-related mutations.

5.4.2 Description of how privacy and confidentiality of medical information/biological specimens will be maximized

For any genetic studies performed, the results will be deposited in a database such as dbGaP per NIH requirements. Although there is controlled access to such a database, such a submission

carries theoretical risks of revealing the identity of the subject. This is discussed in the consent. Confidentiality for genetic samples will be maintained as described (Section [6.1](#)).

5.4.3 Management of Results

Subjects will be contacted if a clinically actionable gene variant is discovered. Clinically actionable findings for the purpose of this study are defined as disorders appearing in the American College of Medical Genetics and Genomics recommendations for the return of incidental findings that is current at the time of primary analysis. (A list of current guidelines is maintained on the CCR intranet: <https://ccrod.cancer.gov/confluence/display/CCRCRO/Incidental+Findings+Lists>).

5.4.4 Genetic Counseling

Subjects who remain on the study will be contacted at this time with a request to provide a blood sample to be sent to a CLIA certified laboratory. If the research findings are verified in the CLIA certified lab, the subject will be offered the opportunity to come to NIH (at our expense) to have genetic education and counseling to explain this result. If the subject does not want to come to NIH, a referral to a local genetic healthcare provider will be provided (at their expense).

This is the only time during the course of the study that incidental findings will be returned. No interrogations regarding clinically actionable findings will be made after the primary analysis.

6 DATA COLLECTION AND EVALUATION

6.1 DATA COLLECTION

The PI will be responsible for overseeing entry of data into a 21 CFR Part 11-compliant data capture system provided by the NCI CCR and ensuring data accuracy, consistency and timeliness. The principal investigator, associate investigators/research nurses and/or a contracted data manager will assist with the data management efforts. Primary and final analyzed data will have identifiers so that research data can be attributed to an individual human subject participant.

All adverse events, including clinically significant abnormal findings on laboratory evaluations, regardless of severity, will be followed until return to baseline or stabilization of event.

Document AEs from the first study intervention, study day 1, through 28 days after the subject received the last product administration. After 28 days, only adverse events which are serious and related to the study investigational agent need to be recorded.

An abnormal laboratory value will be recorded in the database as an AE **only** if the laboratory abnormality is characterized by any of the following:

- Results in discontinuation from the study
- Is associated with clinical signs or symptoms
- Requires treatment or any other therapeutic intervention
- Is associated with death or another serious adverse event, including hospitalization.
- Is judged by the Investigator to be of significant clinical impact
- If any abnormal laboratory result is considered clinically significant, the investigator will provide details about the action taken with respect to the test drug and about the participant's outcome.

End of study procedures: Data will be stored according to HHS, FDA regulations, and NIH Intramural Records Retention Schedule as applicable.

Loss or destruction of data: Should we become aware that a major breach in our plan to protect subject confidentiality and trial data has occurred, this will be reported expeditiously per requirements in Section [7.2.1](#).

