2.3.1 Screen Failures

Screen failures are defined as participants who consent to participate in the clinical trial but are not subsequently assigned to the study intervention or entered in the study. A minimal set of screen failure information is required to ensure transparent reporting of screen failure participants, to meet the Consolidated Standards of Reporting Trials (CONSORT) publishing requirements and to respond to queries from regulatory authorities. Minimal information includes demography, screen failure details, eligibility criteria, and any serious adverse event (SAE).

Individuals who do not meet the criteria for participation in this trial (screen failure) because of a laboratory test abnormalities or non-measurable disease may be rescreened.

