2.4 BASELINE EVALUATION

All participants are required to complete baseline evaluations within the below designated intervals prior to the first planned dosing of the study drug.

Tests performed during screening or on another NIH protocol within the designated time frame before first dose of the study drug do not need to be repeated for the baseline evaluation, unless otherwise indicated:

Within 28 days prior to first dose:

- Baseline research tumor biopsy (optional; does not need to be repeated if biopsy was done during screening or if performed on another NIH protocol)
 - If intranasal disease is present and amenable, endoscopic endonasal tumor biopsy will be performed in an out-participant clinic setting.
 - Core needle biopsy of metastatic disease will be performed, if present and amenable (see Section [5.2.2](#)).

Within 14 days prior to the first dose:

[figure not shown]
- Clinical evaluations:
 - Medical history (interim, signs and symptoms); review of concomitant medications and symptoms/side effects; assessment of performance status
 - Physical examination, including weight, vital signs (i.e., temperature, blood pressure, heart rate, respiratory rate, oxygen saturation with pulse oximetry), and skin assessment
- Laboratory evaluations:
 - Urine or serum pregnancy test (β -HCG) for WOCBP (see Inclusion Criteria [2.1.1.7](#) for definition of WOCBP)

- CBC with differential
- Coagulation panel: PT, INR, PTT/aPTT
- Serum biochemical profile:
 - Acute care panel (Na⁺, K⁺, Cl⁻, CO₂, creatinine, glucose, urea nitrogen)
 - Mineral panel (albumin, calcium total, magnesium total, phosphorus)
 - Hepatic panel (AST/GOT, ALT/GPT, total bilirubin, direct bilirubin, alkaline phosphatase)
- CRP
- LDH
- Amylase, lipase
- Urinalysis
- Thyroid function tests: thyroid stimulating hormone (TSH) and free thyroxine (FT4)
- Research blood samples for correlative studies. Please refer to Section [5](#) for details.

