8.1.6 Adverse Events of Special Interest (AESI)

An adverse event of special interest (AESI) is one of scientific and medical interest specific to understanding of the Investigational Product(s) and may require close monitoring and rapid communication by the investigator to the sponsor. An AESI may be serious or non-serious. The rapid reporting of AESIs allows ongoing surveillance of these events to characterize and understand them in association with the use of these investigational products.

Only AESIs that match the definition of SAE will be reported as other SAEs within 7 days from the knowledge of event. Other non-SAE AESIs should not be reported to OSRO but only collected in the clinical database.

The adverse events related to following, regardless of site, will be collected as an AESI to enable evaluation of potential risk factors, such as site/past radiation/associated infection at site/recent instrumentation and other variables such as time to onset, exposure history, grade of bleeding, anatomical sites, etc. can be collected.

- Mucosal bleeding
- Cutaneous lesions possibly due to TGF-beta

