8.2 ASSESSMENT OF SAFETY EVENTS

AE information collected will include event description, date of onset, assessment of severity and relationship to study product and alternate etiology (if not related to study product), date of resolution of the event, seriousness and outcome. The assessment of severity and relationship to the study product will be done only by those with the training and authority to make a diagnosis and listed on the Form FDA 1572 as the site principal investigator or sub-investigator. AEs occurring during the collection and reporting period will be documented appropriately regardless of relationship. AEs will be followed through resolution.

SAEs will be:

- Assessed for severity and relationship to study product and alternate etiology (if not related to study product) by a licensed study physician listed on the Form FDA 1572 as the site principal investigator or sub-investigator.
- Recorded on the appropriate SAE report form, the medical record and captured in the clinical database.
- Followed through resolution by a licensed study physician listed on the Form FDA 1572 as the site principal investigator or sub-investigator.

For timeframe of recording adverse events, please refer to Section [6.1](#).

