10.3.1 Evaluable for Toxicity

All participants will be evaluable for toxicity from the time of their first treatment with bintralusp alfa.

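### Adverse-event recording opens at the first dose, after the protocol's own optional research biopsy, so biopsy harms before dose 1 in participants who are later treated fall outside the AE record

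*Combined protocol and SAP*

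**What the plan says.** **The window.** Section 6.1 instructs staff: "Document AEs from the first study intervention, study day 1, through 28 days after the subject received the last product administration". Section 8.2 refers back to 6.1 for the timeframe and adds that "AEs occurring during the collection and reporting period will be documented appropriately regardless of relationship". In the study calendar (Section 3.7) the adverse-events row is first marked at Week 1. Section 10.3.1 reads "All participants will be evaluable for toxicity from the time of their first treatment with" the study drug.

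**The biopsy.** Section 2.4, under the heading "Within 28 days prior to first dose", lists: "Baseline research tumor biopsy (optional; does not need to be repeated if biopsy was done during screening or if performed on another NIH protocol"). Where intranasal disease is present and accessible, "endoscopic endonasal tumor biopsy will be performed in an out-participant clinic setting"; otherwise a metastatic site may be sampled by core needle. Section 12.5.1.2 names pain and bleeding among the risks. Calendar footnote 11 gives the baseline biopsy window as 2 weeks before first treatment, not 28 days.

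**Screen failures.** Section 2.3.1 keeps pre-dose serious events for this group: "Minimal information includes demography, screen failure details, eligibility criteria, and any serious adverse event (SAE").

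**Bleeding.** Section 8.1.6 makes mucosal bleeding an AE of special interest and lists among the risk factors to be examined "site/past radiation/associated infection at site/recent instrumentation". Section 10.4.3 tabulates treatment-emergent AEs without defining the term.

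**The concern.** The biopsy is an intervention of this protocol with a stated harm, and it takes place before the AE window opens. A bleed or other complication in that interval is a cost of taking part in the research and belongs in the account of the trial's safety. As written, whether a serious one is kept depends on what happens next: it is kept if the participant fails screening, and no rule keeps it if the participant is treated.

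The gap touches the event of most interest. The biopsy may be taken from nasal tissue, epistaxis is a presenting symptom of the disease (Section 1.2.1), and mucosal bleeding is an AE of special interest. Attribution also feeds into conduct: Section 3.4.4 refers to hemorrhage caused by the drug, and the bleeding table in Appendix B turns on whether another explanation exists. The safety tables would be easier to read if bleeding present before dose 1 were recorded on the same scale as bleeding after it.

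**Working it through.** The plan states no figure on this point, so the check is mainly a comparison of sections.

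**1. When does recording start?** The phrase about the first study intervention in 6.1 could be read as including a biopsy. Three things point to the first dose instead: the same sentence equates it with study day 1, the calendar starts the AE row at Week 1, and 10.3.1 starts toxicity evaluability at first treatment. The AE definition in 8.1.1 is also framed around a participant who has been given a product.

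**2. What comes before it?** The optional baseline research biopsy (2.4), up to 28 days or up to 2 weeks earlier depending on which section is followed. A diagnostic biopsy during screening is also possible (2.2.2).

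**3. Does anything extend recording backwards?** Nothing in 6.1, 8 or 10.4.3 does. Section 8.3 requires SAE reporting, but with the elements of 8.2, which takes its timeframe from 6.1. Section 4 records concomitant medication from 30 days before the first dose, so a drug given for a biopsy bleed could be on file with no matching event.

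| Event | In the AE record as written? |
|---|---|
| SAE in a screen failure | Yes (2.3.1) |
| SAE between biopsy and dose 1, participant later treated | No rule captures it |
| Non-serious biopsy AE before dose 1, participant later treated | No |
| Bleed after an on-treatment biopsy | Yes (6.1) |

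**4. What is known before dose 1?** Symptoms are reviewed at screening within 28 days (2.2.2) and again at baseline within 14 days (2.4). The calendar has an examination with signs and symptoms at screening, baseline and Week 1. Recent significant bleeding, within 3 months, appears among the exclusions (2.1.2.6). None of these requires nasal bleeding to be CTCAE-graded as a baseline value.

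**5. Scale.** Planned participants: 21 + 8 = 29; with 3 inevaluable, the ceiling is 32 (10.2). The documents give no rate of bleeding after this biopsy and no expected uptake. Taking both as assumptions, expected pre-dose bleeds = 29 × uptake × bleed rate:

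| Assumed bleed rate | All biopsied | Half biopsied |
|---|---|---|
| 5% | 29 × 0.05 = 1.5 | 0.7 |
| 10% | 29 × 0.10 = 2.9 | 1.5 |
| 20% | 29 × 0.20 = 5.8 | 2.9 |

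For comparison, the pooled epistaxis rate on drug in Section 14.1.2 is 12%, and 0.12 × 29 = 3.5. That rate comes from other tumor cohorts and says nothing about biopsy bleeding; it shows only that the two counts could be of similar order under these assumptions.

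**The case against.** The strongest reply is that the protocol already has most of what is needed to interpret a bleed. Symptoms are taken at screening, baseline and Week 1, and recent significant bleeding is screened for. For every recorded AE, 8.2 asks for onset date, relationship and, if unrelated, another cause. Section 8.1.6 provides for collecting recent instrumentation, time to onset and anatomical site. This stands. A reader might infer that nasal bleeding on drug has no pre-dose background, or that a biopsy bleed continuing past day 1 cannot be told from a drug bleed. The documents support neither: a bleed with onset before dose 1 and a known biopsy can be recognized as such. What is missing is a graded baseline and a definition of treatment-emergent that uses it.

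Second, the biopsy may be done under another NIH protocol (2.4), and co-enrolment in a biospecimen-procurement study is mandatory (2.1.1.15). The AE rules of those studies are not in these documents, so for such biopsies a loss of data is not shown. Likewise, Section 7.2 relies on institutional policies that cannot be seen here, so it is not shown that a serious pre-dose event would go unreported to oversight bodies. Both points stand, but neither puts the event into this trial's AE data.

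Third, opening the AE window at first dose fits the definition in 8.1.1, and the safety analysis is descriptive. This limits the consequence; it does not explain why SAEs are kept for screen failures and not for treated participants.

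**Conclusion.** The point holds in a limited form. For a biopsy done under this protocol before dose 1, procedure-related AEs and SAEs in participants who are later treated are outside the stated AE record. This rests on reading the start of the window as the first dose, which the calendar and 10.3.1 support.

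Two larger readings should be avoided. Biopsy bleeding in general is not lost, since on-treatment biopsies fall inside the window and screen-failure SAEs are kept. Nor can a shift in the epistaxis rate be claimed: one event in 21 is 1/21 = 4.8 points for any event whatever, and is not evidence about biopsy bleeding.

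The effect is confined to the descriptive safety data in at most 32 participants, and fewer in practice because the biopsy is optional. The response rate, the two-stage rule and its error rates do not use these data and are unaffected. It is an inexpensive improvement, not a threat to the trial's conclusion.

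**What to change.** - **Section 6.1:** record SAEs and AEs related to study procedures from the first protocol-specific procedure, including a baseline research biopsy done under this protocol, and all AEs from study day 1. State explicitly that study day 1 is the first dose. Record any nasal bleeding present before dose 1 with its CTCAE grade.
- **Section 10.4.3:** define treatment-emergent relative to the pre-dose state, and tabulate pre-dose procedure-related events separately from treatment-emergent ones.
- **Section 2.4 and calendar footnote 11:** reconcile the baseline biopsy window, given as 28 days in one and 2 weeks in the other.

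The cost is a few sentences and a few extra pre-dose entries. Sample size, visits and the primary analysis do not change.
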